#### 4.6.2.1.8. Peripheral Edema

The peripheral edema will be searched by MedDRA PTs (see Section 6.7) from all TEAEs. The number and percentage of participants experiencing treatment-emergent peripheral edema will be summarized by PT.

#### 4.6.2.1.9. *Hypokalemia*

The TEAEs of hypokalemia will be identified by narrow terms in Hypokalaemia SMQ (20000233). A summary of the number of participants with TEAEs meeting the SMQ narrow search criteria will be provided by PT.

## 4.6.2.1.10. Hyperglycemia

The study treatments were designed as the treatment of hyperglycemia for diabetes patients. Therefore, the hyperglycemia is usually not reported as an AE in diabetes studies. However, if a participant develops severe, persistent hyperglycemia after randomization, a rescue therapy will be considered. A listing of participants who receive rescue medication will be provided.

#### 4.6.2.1.11. Major Adverse Cardiovascular Events (MACE)

Potential cerebrocardiovascular events will be identified by the investigative site or by a medical review conducted by the sponsor or designee. A blinded external Clinical Event Committee will adjudicate the events in a consistent and unbiased manner. Events include:

- Death
- Cardiac ischemic events including
  - o myocardial infarction
  - o hospitalization for unstable angina
- cerebrovascular events including
  - o stroke
  - o transient ischemic attack
- hospitalization for heart failure, and
- coronary revascularization procedure

Only confirmed MACE by the adjudication committee will be considered as AESIs. A listing of MACE events reported by investigator, including reported term and adjudication results, will be provided.

#### 4.6.2.1.12. Medication Error of Interest

Medication Errors of Interest (MEI) are defined as medication error AEs (SMQ 20000224 - narrow and broad terms) that meet the criteria of important protocol deviations (IPD) indicative of multiple dose, according to the Trial Issue Management Plan (TIMP). These events are considered IPDs and of special interest because of their potential to impact participant's safety.

MEI AEs are categorized as IPDs of "Investigational Medicinal Product and/or Investigational Device". Screening and identification of MEI AEs will occur during routine review of individual trial protocol deviations and trial level safety reviews.

The number and percentage of participants reported with MEI will be analyzed.

A listing of MEI will be provided. This listing will indicate if severe hypoglycemia or P-R hypoglycemia occurred after the MEI.

## 4.6.3. Additional Safety Assessments

## 4.6.3.1. Participant-Reported Hypoglycemic Events

The following types of hypoglycemia events will be derived in the analysis data sets: documented hypoglycemia as Level 1, Level 2, and Level 3 (severe hypoglycemia) according to definitions based on the American Diabetes Association criteria where:

- Level 1: glucose <70 mg/dL (3.9 mmol/L) and ≥54 mg/dL (3.0 mmol/L);
- Level 2: glucose <54 mg/dL (3.0mmol/L);
- Level 3: severe hypoglycemia (confirmed by the investigator to be an event that required assistance for treatment).

Level 2 and Level 3 events are considered clinically significant hypoglycemia. Therefore, the analysis on a composite of Level 2 and Level 3 (denoted as Level 2/3) hypoglycemia will also be conducted.

The hypoglycemia will also be further classified into

- nocturnal hypoglycemia (occurs between midnight and 0600)
- non-nocturnal hypoglycemia (occurs between 0600 and midnight)

If a hypoglycemic event is within 60 minutes of another hypoglycemic event, it is considered as a continuation of the previous event. If there are multiple hypoglycemic events within 60 minutes of each other, then all events will be combined into a single event, which has the

- earlier date time
- minimum glucose value, if applicable
- maximum severity (Level 1, 2 or 3)
- combined symptoms and outcomes, and
- time of nocturnal if any of the events is nocturnal

of the multiple hypoglycemic events.

The combined event starts from the first records with Level 1, 2 or 3, and ends when there are no more events for at least 60 minutes.

The evaluation of potential persistent-recurrent hypoglycemia events will be through assessment of the clinically significant events confirmed by investigators based on clinical judgment and through events identified by a pre-specified criteria described in Section 4.6.2.1.2 and Appendix 9 (Section 6.9) using information based on the participant-reported hypoglycemia.

The details of planned analyses are provided in the below table.

Endpoint	Analysis Period*	Statistical Method
Event rate of Level 1	Baseline, 0-16, 0-26, 0-52, 16-26,	Negative binomial regression with
hypoglycemia events	26-52 weeks, post-treatment period	treatment and baseline HbA1c as
(events/participant/year):		covariates, log (exposure/365.25
All documented		days) as the offset in the model.
Event rate of Level 2	Baseline, 0-16, 0-26, 0-52, 16-26,	Negative binomial regression with
hypoglycemia events	26-52 weeks, post-treatment period	treatment and baseline HbA1c as
(events/participant/year):		covariates, log (exposure/365.25
All documented		days) as the offset in the model.
		If the number of events is too small
		to run the negative binomial
		regression, exposure-adjusted rate
		calculated by total number of events
		divided by total exposure for
		individual patients will be provided
		and the empirical method (see
		Appendix 8 [Section 6.8] for
		details) will be used for treatment
		comparison.
Event rate of Level 3	Baseline, 0-26, 0-52, 26-52 weeks,	Negative binomial regression with
hypoglycemia events	post-treatment period	treatment and baseline HbA1c as
(events/participant/100 year):		covariates, log (exposure/36525
All documented		days) as the offset in the model.
		If the number of events is too small
		to run the negative binomial
		regression, exposure-adjusted rate
		calculated by total number of events
		divided by total exposure for
		individual patients will be provided
		and the empirical method (see
		Appendix 8 [Section 6.8] for
		details) will be used for treatment
		comparison.

Endpoint	Analysis Period*	Statistical Method
Event rate of Level 2/3	Baseline, 0-16, 0-26, 0-52, 16-26,	Negative binomial regression with
hypoglycemia events	26-52 weeks, post-treatment period	treatment and baseline HbA1c as
(events/participant/year):		covariates, log (exposure/365.25
All documented		days) as the offset in the model.

 
Nocturnal
 
		
Non-nocturnal		If the number of events is too small
		to run the negative binomial
		regression, exposure-adjusted rate
		calculated by total number of events
		divided by total exposure for
		individual patients) will be provided
		and the empirical method (see
		Appendix 8 [Section 6.8] for
		details) will be used for treatment
		comparison.
		The plots of the mean cumulative
		functions (MCFs) by each treatment
		arm will also be created. The
		population mean for cumulative
		number of events up to time $t$ , $M(t)$ ,
		will be estimated using a
		nonparametric estimation method
		described by Nelson (2003).
Incidence of Level 1	Baseline, 0-16, 0-26, 0-52, 16-26,	Logistic regression with treatment
hypoglycemia events:	26-52 weeks, post-treatment period	and baseline HbA1c as covariates.
All documented		
Incidence of Level 2	Baseline, 0-16, 0-26, 0-52, 16-26,	Logistic regression with treatment
hypoglycemia events:	26-52 weeks, post-treatment period	and baseline HbA1c as covariates.
All documented		
Incidence of Level 3	Baseline, 0-26, 0-52, 26-52 weeks,	Logistic regression with treatment
hypoglycemia events:	post-treatment period	and baseline HbA1c as covariates.
All documented		
Incidence of Level 2/3	Baseline, 0-16, 0-26, 0-52, 16-26,	Logistic regression with treatment
hypoglycemia events:	26-52 weeks, post-treatment period	and baseline HbA1c as covariates.
All documented		
Nocturnal		
Non-nocturnal		

Endpoint	Analysis Period*	Statistical Method
Potential persistent-recurrent	Safety analysis period (see	The number of participants with at
hypoglycemia events	definition in Section 4.6)	least one event will be summarized

 
identified by
 
		and compared by Fisher's exact test.
investigator		The number of events will also be

 
identified by pre-
 
		provided.
criteria (defined in		
Appendix 9		
[Section 6.9])		

Abbreviations: HbA1c = hemoglobin A1c; Level 2/3= Level 2 and Level 3 composite; mITT = modified Intent-to-Treat.

Note: The hypoglycemia yearly rate during defined period is calculated by the number of hypoglycemia within the period/number of days patient at risk within the period times 365.25. For rare events, 100-year rate will be provided. The hypoglycemia incidence during defined period indicates if the patient has at least 1 hypoglycemia events within the period (Yes/No).

A sensitivity analysis will be done for selected hypoglycemic endpoints where all hypoglycemic events are considered one hypoglycemic event until a subsequent glucose value is  $\geq 70 \text{ mg/dL}$ .

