## 6.3. Measures to Minimize Bias: Randomization and Blinding

#### Randomization and stratification

All participants will be centrally assigned to randomized study intervention using an IWRS. Before the study is initiated, the login information and directions for the IWRS will be provided to each site.

Participants will be randomly assigned in an 1:1 ratio to LY3209590:insulin glargine.

Participants will be stratified based on

- country
- HbA1c stratum at Visit 1 (<8% and  $\ge8\%$ ), and
- GLP-1 RA use at randomization, regardless of oral or injectable administration, (Yes/No).

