### Analysis model

After the imputation, the observed and imputed data will be analyzed by the ANCOVA. The model will include treatment (LY3209590 and insulin glargine), strata (country, GLP-1 RA treatment at randomization), and baseline value of the dependent variable. The statistical inference will be based on the multiple imputation framework by Rubin (1987).

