# 1.1. Objectives, Endpoints, and Estimands

Objectives	Endpoints
Primary	
Demonstrate noninferiority of LY3209590 compared to insulin glargine for the treatment of T2D in adults	Change in HbA1c from baseline to Week 52
Key Secondary (Gated)	
Demonstrate superiority of LY3209590 compared to insulin glargine	Change in HbA1c from baseline to Week 52
Other Secondary	
Compare the effect of LY3209590 to insulin glargine in parameters of glycemic control	
 
Change from baseline to Week 26 for HbA1c
 
Change from baseline to Weeks 16, 26, and 52 for fasting glucose measured by SMBG
 
Insulin dose at Weeks 16, 26, and 52
 

Compare the effect of LY3209590 to insulin glargine on safety endpoints	
 
Incidence and rate of composite of Level 2 and 3 hypoglycemia events during the treatment period
 
Incidence and rate of composite of Level 2 and 3 nocturnal hypoglycemia events during the treatment period
 
Change from baseline to Weeks 26 and 52 in body weight
 

Compare the effect of LY3209590 to insulin glargine on patient-reported outcomes questionnaires	
 
Change from baseline to Weeks 26 and 52 for:
 
TRIM-D, and
 
DTSQ
 
Treatment experience at Weeks 26 and 52 for:
 
DID-EQ, and
 
SIM-Q
 

Tertiary/Exploratory	
Compare the effect of LY3209590 to insulin glargine for efficacy parameters	
 
Percentage of participants at Week 52 achieving:         
 
HbA1c <7%
 
HbA1c <7% without Level 2 or 3 nocturnal hypoglycemia, and
 
HbA1c ≤6.5% without Level 2 or 3 hypoglycemia
 
 
 
Change from baseline to Weeks 26 and 52 for fasting serum glucose
 

Evaluate the percentage of participants receiving LY3209590 that require a transition to the LY3209590 prefilled pen	Percentage of participants that require transition to the LY3209590 prefilled pen at Weeks 26 and 52
Evaluate the percentage of participants at each fixed LY3209590 dose level	Percentage of participants at each fixed dose level at Weeks 26 and 52

Objectives	Endpoints
Compare the effect of LY3209590 to insulin glargine for safety parameters	
 
Incidence and rate of Level 2 hypoglycemia events during treatment period
 
Incidence and rate of Level 3 hypoglycemia events during treatment period
 
Incidence of positive LY3209590 treatment-emergent antidrug antibodies
 

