# 1.2. Study Design

- This is a Phase 3, parallel-design, open-label, randomized control, treat-to-target study to evaluate the efficacy and safety of LY3209590 administered once-weekly compared to insulin glargine administered daily in adult participants with T2D that are insulin naïve.
- The study includes a 3-week screening and lead-in period, a 52-week treatment period, and a 5-week safety follow-up period after the last visit in the treatment period.
- Participants will be randomly assigned to receive daily insulin glargine or weekly insulin LY3209590. Stratification will be by country, HbA1c stratum at Visit 1 (Week -3) (<8.0%, ≥8.0%), and GLP-1 RA use at randomization, regardless of oral or injectable administration.
  - o Participants randomly assigned to insulin glargine
    Participants randomly assigned to insulin glargine will start on 10 U/day and will
    have weekly dose adjustments based on FBG and hypoglycemia events.
  - Participants randomly assigned to receive LY3209590
     Participants randomly assigned to receive LY3209590 will be on a fixed dose escalation for at least the first 16 weeks of the study. Participants will start LY3209590 on a fixed dose of 100 U per week and will escalate the LY3209590 dose every 4 weeks as required to the set doses of 150, 250, and 400 U per week.

Treat-to-target dose adjustments will be based on FBG of 80 to 130 mg/dL (4.4 to 7.2 mmol/L) and hypoglycemia events.

Dose administration will be via a fixed dose autoinjector.

After Week 16, if a participant who has received the fixed dose of 400 U per week for at least 4 weeks has a median FBG level >130 mg/dL, then the investigator should transition the participant to titratable doses using a prefilled pen. This will provide more dosing flexibility and allow dose titrations above 400 U per week.

If a participant transitions from the fixed dose autoinjector to a prefilled pen, they must continue using the prefilled pen for the remainder of the study.

• Rescue therapy will be considered during the treatment period if the participants meet the protocol criteria of severe, persistent hyperglycemia.

If a participant is transitioning to a prefilled pen, investigators should:

- o ensure that the transition does not occur at the same time as initiation of rescue therapy, and
- o wait for at least 4 weeks after the first dose with the LY3209590 prefilled pen.

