## 4.7.2.2. Subgroup Analyses in Hypoglycemia

Subgroup analyses in documented Level 2/3 hypoglycemia, non-nocturnal, and nocturnal hypoglycemia rates during 0 to 52 weeks will be conducted with subgroups defined as:

- Baseline HbA1c stratum (<8.0% and  $\ge8.0\%$ )
- Region (North America and South America)
- Region (US and non-US)
- GLP-1 RA use at randomization
- eGFR at baseline ( $<60, 60 <90, \text{ and } \ge 90 \text{ mL/min/}1.73 \text{ m}^2$ )

The hypoglycemia rates will be analyzed using a negative binomial regression including the same independent variables for hypoglycemia event analyses (see Section 4.6.3.1) plus factors of subgroup, 2-way interaction of subgroup and treatment. Separate analysis without the terms related with the subgroup will be performed for each subpopulation.

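### The Level 2/3 hypoglycemia rate models omit two randomisation strata, GLP-1 RA use and country; adding GLP-1 RA use would gain a little precision

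*SAP*

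**What the plan says.** Protocol 6.3 lists three stratification factors: country, HbA1c at Visit 1 (below 8%, or 8% and above), and "GLP-1 RA use at randomization, regardless of oral or injectable administration, (Yes/No"). SAP 1.2 repeats them.

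SAP 1.1 lists the Level 2/3 endpoint among the other secondary safety endpoints: "Incidence and rate of composite of Level 2 and 3 hypoglycemia events during the treatment period". A nocturnal version follows it. Neither is gated.

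The analysis table in SAP 4.6.3.1 fits the Level 2/3 rate (all documented, nocturnal, non-nocturnal) by negative binomial regression with "treatment and baseline HbA1c as" covariates and log exposure as offset. The incidence rows use logistic regression with treatment "and baseline HbA1c as covariates". If events are too few for the negative binomial model, the Level 2, Level 3 and Level 2/3 rate rows fall back to the empirical method of Appendix 8. The Level 1 rate row and the logistic rows state no fallback.

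By contrast, the primary ANCOVA (Protocol 9.3.2) includes "strata (country, GLP-1 RA treatment at randomization), and baseline value of the dependent variable". SAP 4.7.2.2 names "GLP-1 RA use at randomization" as a subgroup for the Level 2/3 rates, and fits a negative binomial model "including the same independent variables for hypoglycemia event analyses" plus the subgroup and its interaction with treatment.

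**The concern.** An analysis normally carries the factors by which the trial randomises. If such a factor predicts the outcome, including it removes explained variation from the treatment comparison. Here two of the three factors are absent from the models for the main hypoglycemia comparison, without a stated reason, although the SAP uses them in most efficacy models.

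The contrast is sharpest in SAP 4.5.1. The logistic model for reaching an HbA1c target without Level 2 or 3 hypoglycemia adjusts for country, GLP-1 RA use and baseline HbA1c. The same events analysed as an endpoint in their own right are adjusted for baseline HbA1c only. At stake is a small amount of precision in the rate comparison, and a question about covariate choice that is easy to settle before unblinding.

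**Working it through.** **1. The plan's own figures.** The documents give no hypoglycemia rate, dispersion or power. Their only power figures are for HbA1c, with SD 1.1 and 284 completers per arm (670 × 0.85 / 2 = 284.75). The standard error is 1.1 × √(2/284) = 0.0923 and power is Φ(δ/0.0923 − 1.96). This gives 99.1% for δ = 0.4 and 90.1% for δ = 0.3, so the stated figures reproduce. They do not depend on the hypoglycemia models.

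**2. Terms in each model.**

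| Model | SAP section | Country | GLP-1 RA use | HbA1c |
|---|---|---|---|---|
| Primary ANCOVA and MMRM | 4.3.2 | yes | yes | baseline value |
| Insulin dose MMRM | 4.4.2.1 | yes | yes | baseline stratum |
| HbA1c target without Level 2/3 events, logistic | 4.5.1 | yes | yes | baseline value |
| Level 2/3 rate, negative binomial | 4.6.3.1 | no | no | baseline value |
| Level 2/3 incidence, logistic | 4.6.3.1 | no | no | baseline value |
| Level 2/3 rate by GLP-1 RA subgroup, negative binomial | 4.7.2.2 | no | main effect and interaction | baseline value |

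SAP 4.1, SAP 4.6 and Protocol 9.3.5 add no strata to the 4.6.3.1 models.

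**3. Adding GLP-1 RA use alone to the rate model.** All inputs are assumptions except the arm size (670/2 = 335) and the 15% early exit: 45% GLP-1 RA users, base rate 0.5 to 1 event per year, dispersion 2 to 4, 400 simulated trials per setting. The measure is the ratio of mean squared model standard errors of the log rate ratio, with the term over without it.

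- Users at 0.7 times the rate: ratio 0.992 to 0.995, so variance falls by 0.5 to 0.8%.
- Users at 0.5 times the rate: ratio 0.968 to 0.978, so variance falls by 2.2 to 3.2%. Since √0.968 = 0.984, the standard error falls by at most 1.6%.
- A repeat run gave about 0.6 to 0.7% and 2 to 3%, with no loss when GLP-1 RA use has no effect.

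**4. Adding GLP-1 RA use and country together.** Further assumptions: six countries, stratified permuted blocks, dispersion 4, true treatment rate ratio 0.6. Country spread is on the log-rate scale.

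| Control rate per year | GLP-1 RA rate ratio; country spread | Power as planned | Power with strata | Mean SE, planned / with strata |
|---|---|---|---|---|
| 0.3 | 1.0; 0 | 58.0% | 58.0% | 0.232 / 0.231 |
| 0.3 | 0.7; ±0.3 | 56.8% | 56.8% | 0.243 / 0.241 |
| 0.3 | 0.5; ±0.5 | 54.5% | 56.2% | 0.255 / 0.251 |
| 0.7 | 1.0; 0 | 74.5% | 75.0% | 0.193 / 0.192 |
| 0.7 | 0.7; ±0.3 | 71.5% | 73.3% | 0.200 / 0.198 |
| 0.7 | 0.5; ±0.5 | 67.5% | 72.0% | 0.209 / 0.204 |

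The largest gain is 4.5 points. It includes the country effect, so it cannot be credited to GLP-1 RA use alone.

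**5. Type I error.** With no treatment effect, the negative binomial model rejected in 5.2 to 7.5% of trials as planned and in 4.0 to 6.5% with strata. The Monte Carlo standard error is √(0.05 × 0.95 / 400) = 1.1 points. In the 7.5% setting the model with strata also rejected in 6.5%. Both fits there have an empirical SD above the mean model SE (0.254 against 0.239, and 0.249 against 0.234), so the excess is not specific to the omission.

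**6. Incidence models.** Adding GLP-1 RA use alone raised the variance of the log odds ratio by about 0.4 to 0.7% (users at 0.7 times the rate) or 1.0 to 1.9% (0.5 times); a repeat run gave about 0.5 to 1.5%. Power moved by about 1 point or less. With both strata, in the last setting of step 4, the mean log odds ratio moved from −0.352 to −0.363, its SE from 0.195 to 0.198, and power from 44.5% to 45.3%.

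**The case against.** The strongest case for the plan as written has four parts.

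- **Small safety models look like a convention.** The general safety MMRM in SAP 4.6 has no strata either, and it is also used for body weight, another listed secondary endpoint. This stands as an explanation, but the SAP does not state it.
- **The benefit is very small and rests on assumed inputs.** This stands.
- **GLP-1 RA use is already examined in 4.7.2.2.** That is true, and being a listed subgroup does not oblige a factor to be a covariate; eGFR is listed there too. But eGFR is not a randomisation stratum, and the subgroup model does not supply the main estimate. The plan to fit that model also weakens any convergence argument against one main effect in the 0 to 52 week Level 2/3 rate models.
- **Extra terms are risky when events are few.** This stands for Level 3, where the SAP already expects trouble. It also counts against adding country. Section 4.7.2.2 offers two region splits (North/South America and US/non-US), so a region term would need a further choice.

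A reader might infer more than the documents support. It is not true that all randomisation factors are left out: baseline HbA1c stands in for the HbA1c stratum, as in the primary model. Nor does the omission bias the comparison, since randomisation protects it, and the simulations show no type I inflation attributable to it. The precision argument also does not carry over to incidence. The odds ratio is non-collapsible, so an added covariate changes the quantity estimated and slightly raises its standard error.

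**Conclusion.** The point holds in limited form. The Level 2/3 rate models omit GLP-1 RA use and country, both randomisation strata, without explanation. Adding GLP-1 RA use is feasible and would lower the variance of the log rate ratio by about 0.5 to 3% if users have 0.7 to 0.5 times the rate of non-users, with no gain if GLP-1 RA use does not matter. These figures assume 45% users and the rates and dispersions listed above, none of which the documents give. The endpoints are ungated and the planned analysis remains valid, so this is an optional improvement and not a defect that threatens a conclusion. For incidence, the only argument is consistency with the composite model in SAP 4.5.1.

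**What to change.** In SAP 4.6.3.1, add GLP-1 RA use at randomisation (yes/no) as a fixed effect to the Level 1, Level 2 and Level 2/3 negative binomial rate models. Keep the Appendix 8 fallback for Level 2 and Level 2/3. Leave the Level 3 models as planned and do not require a region term.

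The term may also be added to the Level 1, Level 2 and Level 2/3 logistic models to match SAP 4.5.1. If so, the SAP should say that the odds ratio is then conditional on GLP-1 RA use, and should claim no precision gain.

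The subgroup models in 4.7.2.2 inherit the main model's terms, so they would pick up the new one. In the separate analyses within GLP-1 RA subgroups it drops out under the existing rule that subgroup-related terms are omitted.

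The cost is a few words in the SAP and one extra parameter per model. Protocol 9.3.5 fixes no covariates for these models, and Protocol 9.3.1 allows changes that do not affect a principal feature to be made in the SAP. The choice should be fixed before unblinding.
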